1. FINAL PROTOCOL

Overview

This study will enroll 150 older spousally-bereaved adults who are high risk for major depressive disorder (MDD) due to subthreshold symptoms of depression. These subjects will be randomly assigned to digital monitoring of sleep, meals, and physical activity behaviors or enhanced usual care. Subjects will be followed for 12 months after the intervention. We selected a 12-week intervention because this length of time was (a) sufficient to observe change in the proposed mechanism of action (circadian rest activity rhythm); and (b) acceptable to participants in our pilot RCT.

Participants and Study Design

Participants. A total of 150 older adults will be enrolled in the proposed study. We have chosen to target spousally-bereaved adults aged 60 years and older for the following clinical and methodological reasons: (a) adults aged 60 years and older experience bereavement differently than younger age groups because older adults are also experiencing declines in physical, mental, and cognitive health that may inhibit adaptive functioning following bereavement; (b) recently bereaved elders (≤ 12 months post spousal death) are at heightened risk for depression and other mental health problems related to poor self-care; (c) there is an urgency to understand strategies to modify the trajectories of depressive symptoms in bereaved elders already at risk for developing depression (indicated prevention) given the growing population of older adults who become bereaved each year, (d) examining bereaved elders who are at risk for depression is necessary to observe changes in response to the intervention over the short period of time that is

feasible to conduct a RCT. Targeting older adults who are not at risk for depression would increase the likelihood of ceiling effects.

Eligibility Criteria. Inclusion criteria will be (1) aged 60 years and older; (2) spously bereaved within 12 months post-loss; and (3) at-risk for MDD, based on high-risk markers defined as subthreshold symptoms of depression (Hamilton Depression Rating Scale score ≥ 9),¹ together with absence of current MDD, post-traumatic stress disorder, or persistent complex bereavement disorder. Exclusion criteria will be (1) current DSM-5 criteria for syndromal mood, psychosis, or anxiety disorder within the last 12 months; (2) dementia; Modified Mini-Mental State Examination <80 ;² (3) acute suicide risk; based on Herbeck et al. protocol for suicide risk management³; and (4) patients taking new psychotropic medications *after* spousal death to stabilize depression including antidepressants and benzodiazepines >4 days/week for more than two months. Individuals who have been on a stable dose for at least 1 month and agree not to change during participation, unless it is medically necessary, will be included.

[figure not shown]
Recruitment & Screening Strategy. To enroll a total of 150 participants (n=30 in Year 01, n=50 in Years 02-03, n=20 in Year 04), we will take advantage of our network of community partners including: (1) Allegheny Health Network's Healthcare @ Home Hospice Care, (2) primary and specialty medicine at the University of Pittsburgh, (3) faith-based organizations; (4) extensive print and on-air advertising via the UPMC Aging Institute (aging.upmc.com); and (5) University-affiliated research registries (ctsi.pitt.edu). We have successfully recruited participants from each of these partners for the pilot study. We recognize that efforts to recruit adults who are not seeking treatment may be difficult. Recruitment materials will emphasize healthy aging, thereby

encouraging participation by individuals who are interested in health, rather than illness-related research. Once interested participants are identified, they will be scheduled for a clinical assessment during which they will complete a battery of psychosocial questionnaires. Those identified 'at-risk' will be enrolled.

Procedures

Baseline. All participants will receive written *education* about healthy lifestyle choices including pamphlets from the National Sleep Foundation, the US Department of Agriculture's *Choose My Plate*, the NIA's Age Page on *Aging and Alcohol Abuse*, and the NIH's *Getting Fit for Life*. We will help participants to choose a personal *health goal* on which to focus during the study; examples include: (a) engage in 150 minutes of moderate-intensity activity/week; (b) don't skip breakfast; and (c) get 7-8 hours of sleep per night, among others.

Widowed Elders' Lifestyle after Loss (WELL) Intervention Protocol. The WELL intervention is a multicomponent intervention that uses digital monitoring and motivational health coaching to encourage a regular routine of sleep, meals, and physical activity. The combination of self-monitoring, performance feedback, and motivational health coaching will help to ensure the

[figure not shown]
success of study participants. This multicomponent strategy has proven acceptable, with 93% retention in our pilot RCT. **Figure 1** shows the study design.

- ***Digital Monitoring Component.*** We chose to implement an intervention that we hypothesize might reduce depression symptoms via re-entraining a regular routine: behavioral self-monitoring of sleep, meals, and physical activity. Behavioral self-monitoring interventions teach individuals to become mindful of their behaviors and the conditions in which they occur. By increasing awareness and understanding of one's own behavior, improvements in physical activity, dietary behavior, weight status, and sleep have been observed across diverse populations.⁴⁻⁶ Monitoring is usually performed over several months, with individuals recording specific behaviors (e.g., minutes exercising, bedtime/wakeup). Participants randomized to WELL will record the timing of sleep, meals, and physical activity twice daily via Qualtrics on their tablet, smartphone, or PC, for 12 weeks. Tablets will be provided to participants who do not own their own device, to improve the sustainability of a technology-based treatment in population subgroups. The digital diaries includes questions to re-entrain a regular routine; including items from the Pittsburgh Sleep

The image displays the digital monitoring component of the WELL study. On the left, a screenshot of a mobile application titled "Healthy Lifestyle Choices" is shown. It features three main categories: SLEEP (with an orange background and a sunset icon), NUTRITION (with a green background and a meal icon), and EXERCISE (with a blue background and a person running icon). Each category has a list of specific goals or tips. For SLEEP, the tips include: Stick to a sleep schedule – same bed time and wake time 7 days a week, 7-8 hours of sleep per night, Avoid napping throughout the day, and Engage in restful exercise (yoga, meditation) before bed. For NUTRITION, the tips include: Eat 3 or less meals from restaurants per week, Eat on average 2 to 3 meals per day, Focus on VEGETABLES – eat 5 or more servings per day, Focus on WHOLE GRAINS – eat 3+ servings per day, Focus on LEAN Proteins – eat 5 or more of white meat, poultry, seafood, beans, eggs per day, and Focus on CALCIUM – eat 2 to 3 servings of milk, yogurt, cheese, soymilk per day. For EXERCISE, the tips include: 150 minutes of moderate-intensity aerobic activity every week (brisk walking), 75 minutes of vigorous-intensity aerobic activity every week (jogging/running), Physical activity at a moderate or vigorous effort for at least 10 minutes at a time (that is, 100 minutes total per week), Muscle-strengthening activities on 2 or more days a week, and Balance or flexibility activities on 2 or more days a week. At the bottom of this screen, there is contact information for the WELL Research Program: [contact] and [contact], along with links to SLEEP (www.sleep.org), NUTRITION (www.choosemyplate.gov), and EXERCISE (www.cdc.gov/physicalactivity). On the right, a screenshot of a "Sleep Diary: Morning Report" is shown. It asks the participant "Last night I got into bed at this time:" and provides three input fields for "HOUR", "MINUTES", and "AM or PM". Below these fields is a button labeled "Definition: Time I Got into Bed". At the bottom of this screen are three buttons: "Cancel & Go Back", "I'm not sure/skip", and "Next Question".

Diary;⁷ the (1) *Morning Diary* asks about the previous night's sleep including bedtime (hh:mm); time to fall asleep (minutes); number of nighttime awakenings; mood at bedtime (alert, sleepy, worried, anxious; scale 1-10); quality of sleep (scale 1-10); time of morning awakening (hh:mm), time out of bed to start daily activities (hh:mm); and mood at morning awakening (scale 1-10; very good – very bad); the (2) *Evening Diary* asks about physical activity, diet, and sleep behaviors throughout the day including time daily activities started (hh:mm); time of first contact with another person via phone or in-person (hh:mm); time of breakfast, lunch, and dinner (hh:mm); number of servings of whole grains, fruits, vegetables, calcium-rich foods, proteins, and alcohol); number of meals at a sit-down/take out restaurant; number of naps; time spent in light, moderate, and vigorous activity (min); time spent in sitting, walking, muscle strengthening activities (min); and mood throughout the day (scale 1-10; very bad-very good).

- Performance Feedback Component. The WELL intervention includes performance feedback to promote participant engagement and self-knowledge. During the intervention, a web-based “Lifestyle Log” illustrates the timing of and regularity of sleep, meals, and physical over the

last 7 days. User data from the Qualtrics surveys are fed into the Lifestyle Log, creating figures that update in real-time, providing users with up-to-date information about their self-behaviors.

- *Motivational Health Coaching Component.* Improving self-care behavior can be challenging, requiring effort and motivation. Therefore, the effects of self-monitoring to optimize engagement in routine self-care may be enhanced by using motivational interviewing (MI) – a patient-centered approach to strengthen bereaved elders' motivation and commitment to change.⁸ MI facilitates healthy lifestyle change by helping patients resolve ambivalence about change in an empathetic and encouraging climate.^{9,10} During weekly phone conversations, a “lifestyle coach” will use MI techniques (express empathy through reflective listening, develop discrepancy between current situation and future goals, avoid argument, and support self-efficacy) to help strengthen older adults intrinsic motivation to engage in a regular behavioral routine

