We will employ repeated-measures mixed-effects ANCOVA, which extend the standard repeated measures ANCOVA to allow for missing values, error structures other than compound symmetry, and measurements taken non-equal intervals. The test of efficacy for the intervention will be analyzed under an 'intent-to-treat' criteria.¹⁶ We will control for important baseline variables, including baseline levels of the outcome of interest (HAM-D), and, to extend the 'intent to treat' mechanism, all participants randomized into the study are included in all analyses irrespective of protocol violations arising post randomization. Inclusion of covariates may add precision to the estimates and allow us to assess the generalizability of the effects across the covariates. The list of covariates, (e.g., age, sex, race, medical co-morbidity) will be developed prior to any analysis. Statistical significance will be $\alpha=0.05$ (two-tailed). Controlling for baseline variables will allow us to assess both group differences (main effect of group) and for differential change over time for depression symptoms repeatedly over the course of the study (group X time interaction). If the group X time interaction is significant, we will assess in post hoc tests, where the two groups differ. If no group X time interaction, will test main effects only. In all analyses, the time (in days) since spousal death will be included as a covariate.

Missing Data

Missing values are inevitable in clinical research. Participants may drop out from the intervention for a variety of reasons, including time constraints, competing interests, and personal choice. If, despite our projections, there is substantial missing values, we will incorporate the impact of censoring due to lost to follow-up and dropout into the analysis to assess if possible bias exists. We will use pattern mixture models to evaluate if the missing mechanism has an influence on parameter estimates. We will use standard multiple imputation for conducting inference on full data effects. If our data are not missing at random (MAR)¹⁷ (i.e., pattern of ‘missingness’ is similar between groups), we will assess the impact of missingness on our estimates and will use pattern mixture models to check that there are no untoward influences of missing values. Pattern mixture models compare the outcomes (trajectories) across the various patterns of missing data.¹⁸

Sample Size and Power Calculations

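### Does the psychotropic-medication criterion both exclude and include the same person in a way that requires a change to the plan?

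*Combined protocol and SAP*

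**What the plan says.** All the relevant text is in section 1, Final Protocol, under Eligibility Criteria.

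- Exclusion (4) concerns "patients taking new psychotropic medications *after* spousal death to stabilize depression".
- Its frequency and duration limits run straight into the opening of the next sentence: "antidepressants and benzodiazepines >4 days/week for more than two months. Individuals who have been on a stable dose for at least 1 month".
- That next sentence ends with the condition and outcome: those who "agree not to change during participation, unless it is medically necessary, will be included".
- Inclusion (2) requires people to be "spously bereaved within 12 months post-loss", so more than two months of drug use since the loss is possible within the window.
- Exclusion (1) and inclusion (3) separately bar syndromal mood or anxiety disorder in the preceding 12 months and current major depression.

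On analysis, section 3 under Efficacy Analyses says that "all participants randomized into the study are included in all analyses irrespective of protocol violations arising post randomization". Psychotropic use is not mentioned anywhere else in the document.

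**The concern.** Take someone bereaved 8 months ago who started a daily antidepressant for depression 5 months ago, has been on the same dose for 3 months and agrees to keep it. Exclusion (4) says out; the next sentence says in. No connecting word makes the second sentence an exception, and it names no start date that would confine it to drugs begun before the loss.

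Two things could be at stake. First, the readings admit different people: one lets in some who have been medicated for depression since the loss, the other does not. That matters for describing a prevention trial whose outcome is depression symptoms. Second, recruitment runs over four years and several sources, so screeners could apply different readings, and the intent-to-treat rule keeps everyone who is randomized.

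**Working it through.** **Logic of the two sentences.** Code five yes/no conditions: (a) started after the death, (b) more than 4 days a week, (c) more than two months, (d) stable dose for at least 1 month, (e) agrees not to change. The purpose, to stabilize depression, is held as met throughout.

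- All combinations: 2 × 2 × 2 × 2 × 2 = 32.
- Exclusion (4) needs a, b and c, leaving d and e free: 2 × 2 = 4 combinations.
- The stable-dose sentence needs d and e. Of those 4 combinations, exactly 1 also has d and e.

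So the overlap exists, in one profile. The combinations are not equally likely, and the documents give no frequencies, so 1 in 32 or 1 in 4 says nothing about how many participants are affected.

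**Two coherent readings.**

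| Reading of the stable-dose sentence | Contested profile | What exclusion (4) still removes |
|---|---|---|
| Exception to exclusion (4) | In | 3 of its 4 combinations: less than a month on a stable dose, or unwilling to hold it |
| Drugs begun before the death only | Out | All 4 combinations |

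The first is supported by position: a permission directly after a restriction is commonly drafted as its exception. The second is supported by the word *new* and the emphasis on *after* in exclusion (4). Neither reading makes either sentence redundant.

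**Who is left.** Inclusion (2) caps time since the loss at 12 months, so a drug started after the death was started within the period that exclusion (1) looks back over. Anyone who met syndromal mood or anxiety criteria in that period is out on either reading, as is anyone with current major depression. The ambiguity touches only people treated for depression since the loss who met neither bar.

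**Effect on the comparison.** Section 3, Randomization, specifies 1:1 permuted blocks, a sequence concealed from enrolling staff, and allocation requested only after eligibility is decided. Whichever reading a screener applies, and even if screeners differ, the decision precedes allocation and cannot depend on it. Such participants are balanced between arms in expectation.

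**Effect on power.** The stated power is 96.3% with d = 0.616 and α = 0.05. With 150/2 = 75 per arm (an assumption from the 1:1 ratio) and a two-sided two-sample t-test, the result is 0.9631, which reproduces it; the normal approximation gives 0.9650. None of the three inputs is a function of the medication rule, and recruitment continues to 150 (30 + 50 + 50 + 20) under either reading.

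**The case for a change.** The best case for acting is that an eligibility rule should give one answer, that the contested group is defined by treatment for the very condition the trial measures, and that a person once randomized stays in the analysis. A few words would cure it, so why leave it?

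Much of this stands. The overlap is real, no other text settles it, and the investigators do need to reconcile the two sentences so that screening is uniform and the enrolled population can be described.

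The argument from the analysis rule is weaker. Keeping all randomized participants is ordinary intent-to-treat, and the qualifier there concerns violations arising after randomization, whereas an eligibility reading is applied before it. Nor does the width of the eligibility window help: the profile is possible for anyone bereaved between 2 and 12 months, but that is a span of time, not a share of people.

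Adding psychotropic use as a covariate would not settle who is eligible, and no figure in the documents shows what precision it would bring.

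**Conclusion.** No change to the plan follows. This is a scope ambiguity caused by a missing linking phrase, not a rule shown to be wrong. It affects one narrow profile, further thinned by exclusion (1) and inclusion (3), and its frequency cannot be obtained from the documents. Under either reading the randomized comparison stays valid and the power calculation is unaltered; no effect on the estimate is shown.

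The conclusion rests on two assumptions: that eligibility is decided before allocation is known, as the plan states, and that the pilot effect size applies to the enrolled population under either reading. The documents do not say how the pilot handled this criterion, so the second cannot be checked.

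What remains is housekeeping. The two sentences must be reconciled by the investigators, and, if enrolment has begun, a record of the rule applied and the number of randomized participants fitting the profile is enough for reporting. Which reading is right is a clinical matter on which this review takes no position.

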2. FIDELITY MONITORING PLAN

Fidelity to digital monitoring was calculated by summing the number of times participants completed the digital diaries: 2 diaries per day for 3 months = 168 possible diaries. Using the gold-standard for coding fidelity of motivational interviewing – the Motivational Interviewing (MI) Treatment Integrity Coding Manual – four components of MI will be coded during each health coaching session: open-ended questions, affirmations, reflective listening, and summarizing statements.¹¹ All MI sessions were audio recorded and 20% of sessions (from early, middle, and late intervention) were randomly selected for fidelity ratings (by a MI expert) to ensure maintenance of treatment specificity and integrity. The MI expert suggested therapeutic

strategies over the course of contact with participants to ensure fidelity to the desired target – regularity of sleep, meals, and physical activity.

Table 1 shows our fidelity plan for monitoring intervention delivery, receipt, and enactment.¹²

Using the gold-standard for coding fidelity of motivational interviewing – the Motivational

Table 1. Fidelity Monitoring Plan	
Domain	Monitoring procedures
Delivery Is the intervention delivered as intended?	
 - Monitoring checklists for each session (BL, T2, T3, T4, T5) which provide quantification of adherence to session protocols 
Interventionists (for MI)
 
 - Use of a treatment manual - Certified in the use of MI for behavior change by the Motivational Interviewing Network of Trainers (MINT) - Completion of session-by-session tracking forms - Audiotaped sessions
Receipt Did participants receive intervention as intended?	
 - Tracking the # of diaries participants enter in the tablet - Tracking the # of times performance feedback was viewed - Checking in during MI sessions to evaluate what works and what is not working - Identification of any participant barriers to participation (e.g., use of a paper diary in lieu of the tablet because of dexterity barriers)
Enactment Did participants enact the behavioral skills imparted?	
 - Attainment of personal health goal(s) - Follow-up survey of awareness of daily routine - Follow-up survey of continued self-monitoring and progress towards health goal

Interviewing (MI) Treatment Integrity Coding Manual – four components of MI will be coded during each coaching session: open-ended questions, affirmations, reflective listening, and summarizing statements.¹¹ All coaching sessions will be audiotaped and 20% will be randomly selected for fidelity ratings (by a MI expert, [name]) to ensure maintenance of treatment specificity and integrity.¹³ The MI expert will suggest therapeutic strategies over the course of contact with participants to ensure fidelity to the desired target – regularity of sleep, meals, and activity.

3. STATISTICAL DESIGN AND POWER

Descriptive Statistics

Data will be examined descriptively using observed means, standard deviations, and percentiles for continuous variables; and frequencies and proportions for categorical variables. We will

examine continuous variables to determine if distributional assumptions, for e.g., normality and homoscedasticity, are satisfied. Transformations or nonparametric techniques will be applied as needed. Statistical comparisons will be performed to compare the intervention and control arms with respect to demographic characteristics and important health characteristics at baseline. Standard techniques include t-tests for continuous variables and Fisher's exact test and/or Pearson χ^2 procedures for categorical variables. The baseline values of the outcome variables will be analyzed in a similar manner to determine whether any systematic differences between the treatment arms remained after randomization. The proposed study is a randomized clinical trial with repeated measures, with the purpose of (1) assessing change over time for the intervention group relative to the enhanced usual care group and (2) comparing the change between the intervention and enhanced usual care group with regards to the primary outcome (depression symptoms).

Randomization

Groups will be randomized using a 1:1 randomization scheme to minimize threats to internal validity.¹⁴ We will use permuted-block randomization where subjects are allocated randomly within blocks known only to statisticians. Given the possibility of insomnia as an effect modifier we will stratify randomization based on presence of insomnia (Insomnia Severity Index ≥ 10).¹⁵ We will follow the CONSORT 2010 checklist for randomization. Sequence generation: [name] will generate the randomization sequence using the R statistical software. Allocation concealment: the randomization sequence will remain concealed to research staff. Research staff who are enrolling participants will not know the allocation sequence in advance. Implementation: after a participant is determined eligible, research staff will contact [name] about treatment

allocation. *Consideration of sex as a biological variable*: groups will be stratified by sex because women are more likely to experience the death of their spouse compared to men (75% of participants in our pilot RCT were women).

Efficacy Analyses

We will employ repeated-measures mixed-effects ANCOVA, which extend the standard repeated measures ANCOVA to allow for missing values, error structures other than compound symmetry, and measurements taken non-equal intervals. The test of efficacy for the intervention will be analyzed under an 'intent-to-treat' criteria.¹⁶ We will control for important baseline variables, including baseline levels of the outcome of interest (HAM-D), and, to extend the 'intent to treat' mechanism, all participants randomized into the study are included in all analyses irrespective of protocol violations arising post randomization. Inclusion of covariates may add precision to the estimates and allow us to assess the generalizability of the effects across the covariates. The list of covariates, (e.g., age, sex, race, medical co-morbidity) will be developed prior to any analysis. Statistical significance will be $\alpha=0.05$ (two-tailed). Controlling for baseline variables will allow us to assess both group differences (main effect of group) and for differential change over time for depression symptoms repeatedly over the course of the study (group X time interaction). If the group X time interaction is significant, we will assess in post hoc tests, where the two groups differ. If no group X time interaction, will test main effects only. In all analyses, the time (in days) since spousal death will be included as a covariate.

Missing Data

Missing values are inevitable in clinical research. Participants may drop out from the intervention for a variety of reasons, including time constraints, competing interests, and personal choice. If, despite our projections, there is substantial missing values, we will incorporate the impact of censoring due to lost to follow-up and dropout into the analysis to assess if possible bias exists. We will use pattern mixture models to evaluate if the missing mechanism has an influence on parameter estimates. We will use standard multiple imputation for conducting inference on full data effects. If our data are not missing at random (MAR)¹⁷ (i.e., pattern of ‘missingness’ is similar between groups), we will assess the impact of missingness on our estimates and will use pattern mixture models to check that there are no untoward influences of missing values. Pattern mixture models compare the outcomes (trajectories) across the various patterns of missing data.¹⁸

Sample Size and Power Calculations

Power calculations for each aim were calculated assuming effect sizes as estimated from the preliminary data collected in 55 subjects in the PI’s pilot RCT. Calculations were conducted in R using the pwr and powerMediation packages. All tests were conducted at level $\alpha=0.05$. In the preliminary data, a Cohen’s d of 0.616 was observed for the change in depression scores after treatment between WELL and EUC. Under this effect size, there is an estimated 96.3% power to detect differences in changes in depression among treatment groups in Aim 1.

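### Randomisation is stratified by insomnia and sex, but the efficacy model commits to neither as a covariate

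*Combined protocol and SAP*

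**What the plan says.** The combined protocol and SAP, section 3 (Randomization), sets 1:1 permuted-block allocation with two stratification factors. On the first it says: "Given the possibility of insomnia as an effect modifier we will stratify randomization based on presence of insomnia", with insomnia defined as an Insomnia Severity Index of at least 10. On the second, "groups will be stratified by sex because women are more likely to experience the death of their spouse compared to men".

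The Efficacy Analyses text specifies a repeated-measures mixed-effects ANCOVA and firmly commits to two covariates. One is the baseline value of the outcome (HAM-D). The other is time since the death: "In all analyses, the time (in days) since spousal death will be included as a covariate". The rest is left open: "The list of covariates, (e.g., age, sex, race, medical co-morbidity) will be developed prior to any analysis".

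Insomnia does not appear in that text as a covariate, an interaction or a subgroup. Nowhere do the documents say that the analysis will adjust for the stratification factors.

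**The concern.** Stratified blocks force the arms to be nearly balanced on insomnia and sex. If a factor predicts the outcome, that balance reduces the true sampling variance of the treatment effect. A model without the factor leaves its contribution in the residual, so the reported standard error ignores the gain from stratifying. Confidence intervals are then too wide, the actual type I error falls below 5% and power is lost.

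The plan binds itself to days since death in every analysis, but not to the two variables that govern allocation. Insomnia was chosen because it might modify the treatment effect, yet it is not even among the example covariates. What is at stake is precision: the effect estimate stays unbiased and false positives do not rise.

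**Working it through.** **The plan's own figure.** The sample-size text states: "Under this effect size, there is an estimated 96.3% power to detect differences in changes in depression among treatment groups". A two-sided two-sample t-test at alpha 0.05 with d = 0.616 and 75 per arm gives 96.3%, so the figure reproduces. It uses all 150 participants and no covariate adjustment. It is not in dispute.

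**Inputs from the documents.** N = 150, 1:1; alpha 0.05 two-sided; d = 0.616 from the pilot; 93% pilot retention, so 0.93 × 150 ≈ 140 analysed.

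**Assumptions.**
- R² is the share of single-visit residual variance that insomnia explains after the other covariates: 0, 0.05 or 0.10.
- There are four post-baseline visits, inferred from the fidelity table ("Monitoring checklists for each session (BL, T2, T3, T4, T5) which provide quantification of adherence to session protocols"), which does not itself say that HAM-D is taken at each.
- Within-person correlation ρ is 0.5 to 0.7, the insomnia effect is constant over visits, and data are complete.
- The smaller effect is half the pilot value, 0.308. Effects are in single-visit residual SD units.

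**Formulas.** With single-visit residual variance 1, the variance of the analysed outcome is v = 1 for a single visit, or v = ρ + (1 − ρ)/4 for the mean of four visits. This gives 0.625 at ρ = 0.5 and 0.775 at ρ = 0.7.
- SE reported when insomnia is omitted: √(4v/N).
- True SE under stratified allocation: √(4(v − R²)/N).
- SE ratio: r = 1/√(1 − R²/v).
- Type I error when omitted: 2(1 − Φ(1.96r)).
- Power with insomnia included: Φ(d/SE_true − 1.96). Power with it omitted: Φ(d/SE_true − 1.96r).

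**Worked case** (single visit, R² = 0.10, d = 0.308, N = 150). Reported SE = √(4/150) = 0.1633; true SE = √(3.6/150) = 0.1549; r = 1.054; d/SE_true = 1.988. Power included = Φ(0.028) = 0.511; omitted = Φ(1.988 − 2.066) = 0.469. The loss is 4.2 points.

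| Analysis | R² | SE ratio | Type I, omitted | Power at 0.308, omitted / included | Loss (points) |
|---|---|---|---|---|---|
| Any | 0 | 1.000 | 5.0% | equal | 0 |
| Single visit | 0.05 | 1.026 | 4.4% | 0.470 / 0.490 | 2.0 |
| Single visit | 0.10 | 1.054 | 3.9% | 0.469 / 0.511 | 4.2 |
| Four-visit mean, ρ = 0.7 | 0.05 | 1.034 | 4.3% | 0.575 / 0.601 | 2.6 |
| Four-visit mean, ρ = 0.7 | 0.10 | 1.072 | 3.6% | 0.578 / 0.632 | 5.4 |
| Four-visit mean, ρ = 0.5 | 0.05 | 1.043 | 4.1% | 0.671 / 0.701 | 3.0 |
| Four-visit mean, ρ = 0.5 | 0.10 | 1.091 | about 3.3% | 0.679 / 0.740 | 6.1 |

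At d = 0.616 the largest loss in any of these cases is 0.6 points at N = 150 and 0.8 points at N = 140.

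**Simulation check, insomnia omitted.** N = 150, blocks of 4 within insomnia × sex, 50% insomnia (assumed), 75% women (pilot); baseline HAM-D, days since death and sex in both models; 40,000 null trials per scenario. At R² 0, 0.05 and 0.10, rejection of the true null for the group main effect was 4.9%, 4.2% and 3.3% (ρ = 0.5), and 5.0%, 4.2% and 3.9% (ρ = 0.7). With insomnia included it was 4.9% to 5.3%. The mean null estimate was within 0.0015 SD of zero.

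**Simulation check, both factors omitted.** This used a single endpoint and assumed that four fifths of the strata effect comes from insomnia. With the two factors together explaining 10% of variance, type I error was 3.8% omitting both and 4.8% including both. Power at an assumed d = 0.4 was 68.3% and 71.9%. At 5% the figures were 4.9% and 5.4%, and 69.9% and 71.7%.

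**The case against.** The strongest reply is that the covariate list is open and will be fixed before any analysis. Sex is already an example, and a team that stratified on insomnia could well add it. That is true, and it is why the point is a missing commitment. It does not close the gap, because nothing in the text ties the model to the allocation factors.

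Second, the plan looks first at group × time and tests main effects only if there is no interaction. A constant insomnia effect cancels out of the group × time test, so that test is unaffected. This stands. The loss falls on the group main effect and on the by-visit comparisons that follow a significant interaction.

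Third, the harm is small and in the safe direction. The largest figure needs an assumed R² of 0.10 remaining after HAM-D adjustment, half the pilot effect and an assumed visit structure. That also stands, and at R² = 0 there is no loss. Against it, the 0.616 comes from a 55-subject pilot, so a smaller true effect is plausible.

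Two further limits are fair. The pilot d refers to change after treatment, whereas the calculation treats it as an effect in residual SD units, and the two scales need not match. The main table covers insomnia alone, so the cost of omitting sex by itself is not separately established. Neither undermines the case for modelling both factors.

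**Conclusion.** The concern holds. The trial randomises within strata of insomnia and sex, and the current text commits the efficacy model to neither. Validity is not threatened: the likely consequence is a slightly conservative test and some lost precision.

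For R² of 0.05 to 0.10, omitting insomnia makes the standard error 2.6% to 5.4% too wide at a single visit and 3.4% to 9.1% too wide for a four-visit average. Power falls by less than 1 point at the pilot effect and by 2.0 to 6.1 points at half of it. These sizes rest on the assumed R², correlation, visit count and smaller effect. The textual gap rests on no assumption. The change is worth making because it costs almost nothing. The stated 96.3% power is unaffected.

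**What to change.** Add one sentence to Efficacy Analyses: insomnia at baseline (ISI of 10 or more, yes/no) and sex, as used in the randomisation, are fixed covariates in every efficacy model, whatever else is placed on the covariate list. This adds two fixed-effect parameters and uses data already collected to randomise. It needs no new visits or participants.

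A group × insomnia estimate is optional and not part of this fix. If the team wants one, it should be pre-specified as descriptive. With an assumed insomnia share p of 30% to 70%, its SE is √(4/(150p) + 4/(150(1 − p))) = 0.327 to 0.356 SD. Power to detect a difference between strata as large as 0.616 SD would be only 41% to 47%.
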